#### **5.3.2** Exclusion Criteria

All subjects will be excluded from enrollment if they:

- 1. Have a lifetime history of schizophrenia, schizoaffective disorder, or bipolar disorder;
- 2. Have a history of electroconvulsive therapy;
- 3. Have the presence of a metal device (e.g., any type of electronic, mechanical, or magnetic implant; cardiac pacemaker; aneurysm clips; implanted cardiac defibrillator) or potential ferromagnetic foreign body (metal slivers, metal shavings, other metal objects) that are contraindications for MRI;
- 4. Are claustrophobic or otherwise unable to tolerate the imaging procedure (use of mild sedatives are permitted to manage claustrophobia);
- 5. Have current clinically significant cardiovascular disease or clinically significant abnormalities on screening electrocardiogram (ECG) (including but not limited to QTc>450 msec);
- 6. A history of additional risk factors for Torsades de Pointes (TdP) (e.g., heart failure, hypokalemia, family history of Long QT syndrome) or are taking drugs that are known to cause QT-prolongation (a list of prohibited and discouraged medications is provided by the Sponsor);
- 7. Have a current clinically significant infectious disease, endocrine or metabolic disease, pulmonary, renal or hepatic impairment that the investigator believes would affect study participation (i.e. neuropsychological testing) or scan results;
- 8. Have a history of cancer (other than skin or in situ prostate cancer) within the previous 5 years;

- 9. Have current drug or alcohol abuse/dependence;
- 10. Have a history of alcohol abuse/dependence with 2 years of the onset of the symptoms of dementia;
- 11. Are females of childbearing potential who are not surgically sterile, not refraining from sexual activity or not using reliable methods of contraception. Females of childbearing potential must not be pregnant or breastfeeding at screening. Females must agree to avoid becoming pregnant, and both females and males must agree to refrain from sexual activity or to use reliable contraceptive methods for 90 days following administration of F-AV-1451 Injection; and
- 12. In the opinion of the investigator, are otherwise unsuitable for a study of this type.

# 5.4 Prior and Concomitant Therapy

Except as noted in the exclusion criteria, all medications (prescription or over-the-counter) that have been started prior to screening may be continued during the course of the trial. All medications, including investigational medications that are continued from the start of the trial or that are started during the trial (other than the study medication) must be documented on the Concomitant Medication Page of the Case Report Form (CRF).

# 5.5 Removal of Subjects from Trial

Subjects must be removed from the trial if:

- 1. Informed consent is withdrawn; or
- 2. The investigator or the sponsor believes it is in the best interest of the subject to be removed from the trial.

Subjects may be withdrawn from the trial if a SAE occurs. The date and reason for discontinuation should be noted on the CRF. Subjects who discontinue prematurely should be seen for a final evaluation.

#### 5.6 Premature Termination of Trial/Closure of Center

The sponsor may discontinue the trial at any time. Reasons for discontinuation of the trial may include, but are not limited to, new information on safety or efficacy, requests from regulatory authorities, or changes in business priorities. Additional reasons for center closure may include, but are not limited to, excessive protocol violations, inadequate regard for subject safety, failure to follow recommended procedures (e.g., documentation), failure or inability to accommodate Avid/Contract Research Organization (CRO) monitors or to provide required access to data and source documents, staff turnover or inadequate staffing, and inadequate enrollment. Except in cases affecting subject safety, the investigator

may complete final study evaluations for ongoing subjects. In all cases of center or study termination, appropriate steps will be taken to ensure the safety of study subjects.

# 6. WARNINGS/PRECAUTIONS

The most up-to-date and complete information regarding the use of F-AV-1451 Injection can be found in the investigator's brochure.

In brief, F-AV-1451 Injection is an experimental imaging agent that will be used at relatively low (tracer) doses. However, because F-AV-1451 Injection is in the early stages of clinical investigation, it is recommended that subjects receiving F-AV-1451 Injection be followed closely by means of adverse event reporting, vital signs, ECGs, and laboratory tests.

#### 7. PROCEDURES AND METHODS

# **7.1 Assessment Periods (See Section 11.2, Trial Flow Chart)**

The study will consist of the following sequence of activities:

# 7.1.1 Screening Visit:

Subjects currently enrolled in the AIBL (previously had amyloid imaging in the form of florbetapir (F) PET imaging) study will be contacted to participate. Screening may take place over several days. All screening assessments should be performed within 60 days of the initial F-AV-1451 PET imaging session.

Screening assessments will include:

- Informed Consent:
- Demographics (age, gender, race, ethnicity, education, alcohol, drug use and smoking);
- Medical history and concomitant medications;
- Physical and neurological examination;
- Disease history (date/months since symptom onset, date/months since diagnosis) for cognitively impaired subjects;
- Family history of neurologic disease;
- Safety assessments: Vital signs (pulse rate, respiratory rate, supine blood pressure, height and weight), ECG, and safety labs (hematology, chemistry and urinalysis); and
- A physician will see the subject during the screening visit.

#### 7.1.2 MRI Visit

MRI will be acquired within 6 months, either prior or after, the F-AV-1451 PET scan. The subject's AIBL MRI scan can be used as long as it is obtained within this timeframe.

# 7.1.3 F-AV-1451 PET Imaging Visits

# Initial F-AV-1451 PET Imaging Visit:

To optimally compare to the AIBL cognitive evaluation, the F-AV-1451 PET scan will be obtained within +/- 2 months of the planned (or obtained) cognitive evaluation in AIBL.

- A physician must see the subject prior to administration of F-AV-1451 Injection to determine if they are still suitable to undergo the scan;
- Vital signs will be taken (pulse rate, respiratory rate, supine blood pressure) at the following time points:
  - ➤ Immediately prior to administration of F-AV-1451 Injection (Weight will also be collected);
  - ➤ After completion of the 30-minute PET scan prior to discharge;
- Subjects will receive a single IV bolus injection target dose of 240 MBq +/- 10% of F-AV-1451 Injection followed by a saline flush;
- A 5-minute brain scan (1 frame of 5 minute duration) will begin immediately following the administration of F-AV-1451 (however if there are logistical or technical reasons this scan cannot obtained, it will not be a protocol violation);
- At approximately 75 minutes following injection, a continuous 30-minute brain scan (6 frames of 5 minute duration) will begin;
- The injection site will be observed for excessive inflammation or damage to the surrounding tissue where the dose was injected;
- Adverse events will be continuously monitored during the F-AV-1451
  PET imaging visit. Subjects who experience an adverse event will not be
  discharged from the imaging center until the event has resolved or
  stabilized;
- A physician will see the subject prior to discharge from the imaging center to evaluate the subject's readiness for discharge; and
- A follow-up phone call to the subject, or designated decision maker, will be conducted within 2 or 3 business days of the imaging day, but not before 48 hours post-injection, to confirm subject well-being and to collect information about any new adverse events. If both of these days are not business days, the follow-up phone call can occur the following business day.

# Follow-Up F-AV-1451 PET Imaging Visit:

Subjects will have a follow-up F-AV-1451 PET scan at 12 (+/- 3) months following the initial F-AV-1451 scan.

• A physician must see the subject prior to administration of F-AV-1451 Injection to determine if they are still suitable to undergo the scan;

- Vital signs will be taken (pulse rate, respiratory rate, supine blood pressure) at the following time points:
  - ➤ Immediately prior to administration of F-AV-1451 Injection (Weight will also be collected);
  - After completion of the 30-minute PET scan prior to discharge;
- Subjects will receive a single IV bolus injection target dose of 240 MBq +/-10%) of F-AV-1451 Injection followed by a saline flush;
- A 5-minute brain scan (1 frame of 5 minute duration) will begin immediately following the administration of F-AV-1451 (however if there are logistical or technical reasons this scan cannot obtained, it will not be a protocol violation);
- At approximately 75 minutes following injection, a continuous 30-minute brain scan (6 frames of 5 minute duration) will begin;
- The injection site will be observed for excessive inflammation or damage to the surrounding tissue where the dose was injected;
- Adverse events will be continuously monitored during the F-AV-1451
  PET imaging visit. Subjects who experience an adverse event will not be
  discharged from the imaging center until the event has resolved or
  stabilized;
- A physician will see the subject prior to discharge from the imaging center to evaluate the subject's readiness for discharge; and
- A follow-up phone call to the subject, or designated decision maker, will be conducted within 2 or 3 business days of the imaging day, but not before 48 hours post-injection, to confirm subject well-being and to collect information about any new adverse events. If both of these days are not business days, the follow-up phone call can occur the following business day.
- A brief cognitive evaluation will be performed on the day of the follow-up F-AV-1451 scan. If not able to be done on the day of scan it may be done on a separate visit within 2 months of the follow-up scan. The brief cognitive evaluation will consist of the Mini Mental State Examination (MMSE), Clinical Dementia Rating (CDR) scale, the alternative forms of California Verbal Learning Test-II (CVLT-II), Delis-Kaplan Executive Function System (D-KEFS) verbal fluency (letter and category), Boston Naming Test 30 Item, (Taylor) Complex Figure Test and Logical Memory Wechsler Memory Scale Revised.

#### 7.2 Observations and Measurements

#### **Informed Consent**

Potential subjects and legally authorized representatives, if applicable, will be allowed to read a written informed consent form. The principal investigator or designee will explain all study procedures, risks, and alternative therapies to the subject. The subject will have an opportunity to have all questions answered. The

appropriate parties will then sign and date the informed consent form, indicating willingness to participate in the study (see Section 7.5). A copy of the signed informed consent will be given to the subject or legally authorized representative.

All informed consent forms must be approved by Avid or designee, and by the appropriate Institutional Review Board/Independent Ethics Committee (IRB/IEC) prior to use.

## Medical History, Neurologic Disease History

The investigator or designee will obtain an updated history at the screening visit.

- Relevant demographic information
- Review of body systems
- Social history
- Medical and surgical history
- Concurrent medications
- Neurologic Disease history (date/months since symptom onset and date/months since diagnosis)
- Family history of neurologic disease

Whenever possible, the medical history will be confirmed by medical records.

## **Physical Examination**

A complete physical examination will be conducted at the screening visit. Clinically significant changes from screening will be recorded as adverse events for the relevant study period.

#### Neurological Examination

A neurological examination will be performed at the screening visit to evaluate cranial nerves, gait, sensory, and motor function, coordination and tendon reflexes. The investigator is to look for these specific signs:

- Pyramidal signs (plantar extension reflex, Achilles tendon clonus);
- Extrapyramidal signs (rigidity, wrist cogwheel phenomena, involuntary movements); and
- Myoclonus.

# Vital Signs

Vital signs (pulse rate, respiratory rate, supine blood pressure) will be taken as part of screening and at the following time points:

- F-AV-1451 Imaging Visit
  - o Immediately prior to the administration of F-AV-1451 Injection
  - o After the completion the 30-minute PET scan prior to discharge.

## Height and Weight

At both screening and imaging visits (immediately prior to each F-AV-1451 administration) body weight will be measured, lightly clothed. Height will only be measured at screening.

## Electrocardiogram (ECG)

A resting 12-lead electrocardiogram will be recorded as part of the screening visit.

# Clinical Laboratory Tests

Clinical laboratory evaluation will be performed at screening.

#### Tests will include:

- **Hematology** (5 mL EDTA): hemoglobin, hematocrit, RBC, WBC, MCH, MCHC, neutrophils, bands, lymphocytes, monocytes, eosinophils, basophils, platelets, morphology, MCV, and RBC morphology.
- Chemistry (6 mL blood): total bilirubin, alkaline phosphatase, ALT (SGPT), AST (SGOT), urea nitrogen, creatinine, glucose, uric acid, calcium, phosphorus, total protein, albumin, total cholesterol, triglycerides, sodium, potassium, bicarbonate, chloride, magnesium, globulin, GGT.
- **Urinalysis** (10 mL, urine): Samples will be used to assess glucose, RBC, WBC, specific gravity, pH, protein, ketones, urobilinogen, blood, nitrite, microscopic, color, bilirubin, casts, epithelial cells, leukocyte, esterase, and bacteria.

#### Neuropsychological Testing

A brief cognitive evaluation will be performed on the day of the follow-up F-AV-1451 scan or on a separate visit within 2 months of the follow-up scan. The brief cognitive evaluation will consist of the MMSE (Folstein et al., 1975), CDR (Morris et al., 1993), the alternative forms of California Verbal Learning Test-II (CVLT-II) (Delis et al., 2000), D-KEFS verbal fluency (letter and category) (Delis et al., 2001), Boston Naming Test (BNT) 30 Item (Saxton et al., 2000), (Taylor) Complex Figure Test (Hamby et al., 1993) and Logical Memory – Wechsler Memory Scale – Revised (Wechsler, 1987).

#### Physician Visit

A physician must see the subject at baseline, prior to each F-AV-1451 administration and at study end, prior to discharge from each F-AV-1451 imaging session. At discharge, the physician should review all safety data and briefly examine/query the subject regarding potential adverse events or other treatment issues.

## 7.3 Protocol for Image Collection

The sponsor will prepare and distribute imaging manuals for F-AV-1451 imaging parameters and scan transmission procedures prior to site initiation. The MRI, if applicable, imaging parameters should follow the Alzheimer's Disease Neuroimaging Initiate (ADNI) MRI protocol.

# 7.4 Good Clinical Practice and Monitoring

All clinical studies performed under the direction of Avid/CRO will be conducted in accordance with applicable regulatory requirements and International Conference on Harmonization (ICH) Good Clinical Practice (GCP) and Avid/CRO Standard Operating Procedures (SOP).

#### This includes:

- 1. IRB/IEC approval: An investigation will be initiated at a study site only after the IRB/IEC for that study site has given their written approval of the protocol and informed consent;
- 2. Informed Consent: Study procedures will not be initiated until the subject and/or their legally authorized representative (as appropriate) signs the informed consent form;
- 3. Recording and monitoring of adverse events as outlined in Section 7.7.3 including the notification of study site clinical investigators, local IRBs/IECs and the FDA, TGA or other international regulatory authorities regarding serious adverse event;
- 4. Avid RP's obligation to monitor the participating center on a regular basis; and
- 5. The termination of a center or the trial if conditions apply, as outlined in Section 5.6.

## 7.5 Informed Consent and Subject Information

Potential subjects, or their legally authorized representative (as appropriate), will be allowed to read a written informed consent form. The principal investigator or designee will explain all study procedures, risks, and alternative therapies. The subject and legally authorized representative will have an opportunity to have all questions answered by a physician. The subject will then sign and date the informed consent form, indicating willingness to participate in the study.

If the subject is capable of giving informed consent then the subject should sign on the consent line of the informed consent form. When applicable, the legally authorized representative should sign as well, indicating that they have witnessed the subject's consent, and further agree to participate as an informant.

Subjects with AD are potentially a vulnerable population with compromised mental capacity. Investigators should take extra care to evaluate a patient's ability to give consent. If the subject is not capable of giving consent, consent may be given by a legally authorized representative. However, it is expected that all subjects entering this study should at least have the capacity to understand that they are engaging in a research study and should affirm that they do not object to participating, by signing on the Subject Assent line of the consent form.

All informed consent forms must be approved by Avid or designee, and by the appropriate IRB/IEC. No study related procedures shall be performed prior to completion of the informed consent process, and signing of the consent form. A copy of the signed informed consent should be given to the patient and/or their legally authorized representative for their records.

#### 7.6 Documentation

F-AV-1451 and MRI scans will be saved in an appropriate electronic format as specified in the imaging manuals. A copy of all scans, including the florbetapir (F) and MRI scans conducted in the AIBL study protocol, will be saved at the site/imaging center and a copy of each will be forwarded to the sponsor or to the designated imaging core lab as described in the imaging manuals. All other data required by the protocol will be recorded in the eCRFs. All data in the eCRFs will be substantiated by "source documents," which consist of the subject's medical files, laboratory result sheets, ECG tracings, etc. All source documentation must be available to Avid and designees. Completed source documents and eCRFs may need to be made available and complete for an audit by the FDA or other international regulatory authorities or Avid at any time. CRFs and all other records must be filed in accordance with applicable laws and regulations (see Section 10.6)

# 7.7 Adverse Events (AE)

Avid's standards for recording and reporting adverse events (AEs) are to be followed regardless of applicable regulatory requirements that may be less stringent. All AEs must be fully recorded on the adverse event eCRFs. Investigators will be instructed to report to Avid or its designee their assessment of the potential relatedness of each AE to study drug or protocol procedure via electronic data entry. If a patient's treatment is discontinued as a result of an AE, study site personnel must clearly report to Avid or its designee via electronic data entry the circumstances and data leading to any such discontinuation of treatment. In cases where the investigator notices an unanticipated benefit to the patient, study site personnel should report "unexpected benefit" with the actual event term to Avid or its designee (for example, the complete actual term would be "unexpected benefit- sleeping longer").

Laboratory test abnormalities considered by the Investigator to be clinically relevant should be reported on the adverse event eCRFs. Signs and symptoms of each AE should be described in detail (e.g., start and stop dates/time,

severity/intensity, relationship to study drug, action taken, and outcome). Additionally, any clinically significant findings from laboratory evaluations, vital sign measurements, or other study procedures including those that result in a diagnosis should be reported as an AE to Avid or its designee.

# 7.7.1 Adverse Event Monitoring

Each patient must be carefully monitored for adverse events. This includes clinical laboratory test variables. An assessment must be made of the severity/intensity and relationship to the administration of the study drug.

## 7.7.2 Adverse Event Definitions

#### Adverse Events

An adverse event is any undesirable experience occurring to a subject during a clinical trial, whether or not considered related to the study drug.

For reporting purposes, Avid will distinguish among pre-existing conditions, trial-emergent adverse events and treatment-emergent adverse events.

Pre-existing conditions (i.e., undesirable experiences, signs or symptoms that begin prior to the Screening Visit) will be recorded on the medical history and/or physical exam eCRF pages. During the study, site personnel will record any change in the condition(s) and occurrence and nature of any AEs. Signs and symptoms that are believed to be due to the pre-existing condition under study (started prior to dose of study medication) do not have to be recorded in the AEs section of the eCRF, unless there is an increase in frequency and severity. Additionally, signs or symptoms or changes in pre-exisiting conditions that occur outside the trial defined adverse event reporting period will be recorded in medical history.

An adverse event is any untoward medical occurrence associated with the use of a drug in humans, whether or not considered drug related. For the purposes of this study, untoward medical occurrences will be considered associated with the use of F-AV-1451, and thus be reported as adverse events, if they occur within 48 hours after administration of F-AV-1451. Adverse events associated with the use of F-AV-1451 will be recorded as treatment emergent relative to the respective drug. Adverse experiences that occur after administration of F-AV-1451 but outside the 48 hour reporting window will not be reported unless the investigator believes they are attributable to the drug.

In order to capture possible adverse effects of trial participation, trial-emergent adverse events will also be reported as any untoward medical occurrences occurring, during the study period but not during the 48 hour window following the administration of F-AV-1451. For the purpose of trial-emergent adverse events, the study period will be defined as beginning with the signing of consent and ending immediately before the administration of F-AV-1451.

The end of study for the purpose of adverse event reporting is defined as 48 hours after the administration of F-AV-1451.

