# Serious Adverse Event (SAE)

An SAE is an AE that results in one of the following outcomes or constitutes one of the following events:

- Death;
- Initial or prolonged inpatient hospitalization (other than that required by protocol; "social hospitalization" or any hospitalization for non-medical reasons does not constitute an SAE);
- A life-threatening experience (that is, immediate risk of dying);
- Persistent or significant disability/incapacity;
- Congenital anomaly/birth defect;
- Considered significant by the investigator for any other reason.

Important medical events that may not result in death, be life-threatening, or require hospitalization may be considered serious adverse drug events when, based upon appropriate medical judgment, they may jeopardize the patient and may require medical or surgical intervention to prevent one of the outcomes listed in this definition.

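### Protocol 7.7.2 makes AE entry optional when a symptom of the condition under study worsens after injection in severity only, or in frequency only

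*Protocol*

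**What the plan says.** Protocol 7.7.2, under Adverse Events, begins with a broad definition: "An adverse event is any undesirable experience occurring to a subject during a clinical trial, whether or not considered related to the study drug". It then deals with pre-existing conditions. While the study runs, "site personnel will record any change in the condition(s) and occurrence and nature of any AEs". The next sentence carves out an exemption for symptoms that the site attributes to the disease being studied and that were present before dosing. These "do not have to be recorded in the AEs section of the eCRF, unless there is an increase in frequency and severity".

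The following paragraph of 7.7.2 treats untoward events as associated with the tracer, and so reportable as AEs, "if they occur within 48 hours after administration of" the tracer. SAP 5.3.1 uses the same 48-hour rule to define a treatment-emergent AE and does not repeat the exemption.

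The general recording rules carry no exemption either. Protocol 7.7 states: "All AEs must be fully recorded on the adverse event eCRFs". Sections 7.7.3 and 10.7 say the same in similar terms. Protocol 7.2, under Physical Examination, asks that clinically significant changes since screening be entered as AEs.

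For serious events, protocol 7.7.2 states: "An SAE is an AE that results in one of the following outcomes". Section 7.7.4 requires SAEs to be collected for 48 hours after dosing whatever the investigator thinks of their cause.

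**The concern.** The exemption joins its two conditions with *and*. Suppose a subject with AD and known intermittent confusion has one unusually severe episode 12 hours after injection, and the investigator attributes it to the AD. Severity has risen, but a single episode need not show a rise in frequency. The exemption lets the site leave this off the AE page, while the 48-hour rule tells the site to report it.

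What is at stake is the completeness of the non-serious safety record. Expanding the tracer's safety database is a stated exploratory objective, and protocol section 6 recommends close follow-up because the tracer is at an early stage. In the protocol's flow chart, the ECG, the safety laboratory tests and the physical and neurological examinations are scheduled at screening only. After injection, the scheduled safety information consists of vital signs, observation of the injection site, physician review and AE reports. A neurological or cognitive worsening that is kept off the AE page has no other scheduled safety examination to capture it.

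**Working it through.** No formula applies to the wording, so the check is a literal reading of the exemption set against the other rules.

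**1. What the exemption requires, read literally**

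| Frequency up | Severity up | AE-page entry required by the exemption? |
|---|---|---|
| yes | yes | yes |
| yes | no | no |
| no | yes | no |
| no | no | no |

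The second and third rows are the problem. Both are worsenings, and in both the exemption removes the duty to enter them.

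**2. What the other rules require for those two rows, within 48 hours of injection**

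- Protocol 7.7.2, 48-hour paragraph: report as an AE.
- SAP 5.3.1: report as a treatment-emergent AE.
- Protocol 7.2, Physical Examination: enter as an AE if the change since screening is clinically significant.
- Protocol 7.7, 7.7.3 and 10.7: every AE goes on the eCRF.
- Protocol 7.7.2, pre-existing conditions: changes outside the AE reporting period go to medical history, which suggests that changes inside it belong with the AEs.

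Two people at the site could therefore handle the same event differently, each following the protocol. The definition of an unexpected AE, also in 7.7.2, links severity and frequency with *or*.

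**3. Route into the tables**

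The summaries in SAP 7.5.3 to 7.5.7 count recorded events. SAP Appendix I treats missing intensity as severe, missing seriousness as serious and missing relationship as related. Those conservative rules need a record to act on and cannot restore an event that was never entered.

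**4. Serious events**

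Protocol 7.7.4 collects SAEs to 48 hours with no exception for the condition under study. Section 10.7 requires notification of any serious event, and 7.7.3 adds a separate SAE form. In all four rows above, an event that meets an SAE criterion within 48 hours must still be collected.

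**5. Who is exposed**

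The planned group sizes in the protocol synopsis are about 25 MCI and about 20 AD.

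- Subjects: 25 + 20 = 45 of 120, and 45/120 = 37.5%.
- Injections, if everyone has both scans: 45 × 2 = 90 of 120 × 2 = 240.

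These are headcounts of those most likely to have symptoms of the disease, not counts of lost events.

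**6. What one omission would do**

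If all 120 are dosed and one subject's only event is left off, the overall percentage of subjects with a treatment-emergent AE falls by 1/120 = 0.8 percentage points. The documents give no rate of such worsenings, so no expected number of omissions can be derived.

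**The case against.** The strongest reply is that the clause is permissive and narrow. It lifts a duty and does not forbid entry. It applies only to "Signs and symptoms that are believed to be due to the pre-existing condition under study (started prior to dose of study medication"), so an investigator who doubts that the disease explains the symptom gets no exemption. The duty to record any change names no eCRF page, and 7.7.2 also uses the medical history and physical examination pages. A change can therefore be recorded somewhere without being on the AE page, and that sentence does not flatly contradict the exemption. All of this stands. It limits the point to optional omission, and it moves the real tension to the 48-hour rule, the physical-examination rule and the rules that all AEs go on the eCRF.

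A reader might also infer that SAEs could be lost, because an SAE is defined as a kind of AE. The documents do not support that. The exemption concerns one section of the eCRF. It does not alter the broad definition of an AE, and SAE collection after dosing is required separately.

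Nor do the documents show that the two-part test is almost impossible to meet within 48 hours. No measure of frequency is given, and an extra episode in that window could count as an increase. It remains fair to say that a single worse episode may raise severity without a demonstrable rise in frequency.

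**Conclusion.** The drafting defect is real. Read literally, 7.7.2 lets the site leave a one-dimension worsening of the condition under study off the AE page, in tension with general AE rules that have no such exemption. The consequence is possible under-recording of non-serious treatment-emergent AEs, mainly among the MCI and AD subjects.

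The size is unknown. Any omission would lower the counts, but whether omissions occur depends on how the site applies the exemption. It would be too strong to infer that AE rates in the impaired groups are biased downward as a matter of fact. It also matters that the planned AE summaries (protocol 8.6, SAP 7.5.3 to 7.5.7) specify no breakdown by diagnosis and no comparison between groups, so the exposure is in the overall tables.

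The conclusion rests on the literal meaning of *and*. Some staff may read the clause loosely as *or*, in which case nothing is lost, but the text does not secure that reading. The primary imaging analyses are untouched.

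**What to change.** In protocol 7.7.2, replace *and* with *or* between frequency and severity in the exemption, so that a worsening in either one restores the duty to enter an AE. Reconcile the clause with the 48-hour rule, with the physical-examination rule in 7.2 and with 7.7, 7.7.3 and 10.7, and carry the same wording into the eCRF completion guidance. Optionally, add a cross-reference stating that the exemption does not affect SAE reporting under 7.7.4. That would be a clarification, since the duty already exists.

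The cost is a short protocol edit, a line of guidance and slightly more AE entries.
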